5.3.7. Anti-Emetic Therapy

Nausea is not common with either entospletinib or obinutuzumab. Grade 3 nausea occurred in <4% of patients who received entospletinib on a recent Phase II study [29], thus considered low risk for emetogenesis.

Anti-emetic therapy may be instituted for any patient. Premedication with a single dose of Compazine 10 mg is preferred, and pre-medication with 5-HT3 antagonists (e.g., ondansetron 4-8 mg po) is allowed. Rescue therapy with 5-HT3 antagonists (ondansetron) is allowed according to standard dosing guidelines, not to exceed the maximum daily dose. Other antiemetics (aprepitant, benzodiazepines etc.) may be used as indicated.

5.4 Duration of Treatment

In the absence of treatment delays due to adverse events, treatment will continue for at least 12 cycles (treatment with entospletinib may continue beyond 12 cycles, as noted elsewhere; obinutuzumab will be administered for 6 cycles) or until one of the criteria below applies.

- Disease progression
- Unacceptable adverse event(s),
- Intercurrent illness that prevents further administration of treatment,
- Participant decides to withdraw from the study, or
- Pregnancy, or
- General or specific changes in the participant's condition render the participant unacceptable for further treatment in the opinion of the treating physician.
- Closure of study by sponsor investigator or discontinuation of drug availability.

5.5 Duration of Follow-up

Study participants will remain on study until disease progression, until study drug-related toxicities have resolved or are deemed irreversible by the sponsor-investigator (in discussion with a treating physician), whichever is later, or until the study is closed. If a study participant discontinues study treatment due to reasons other than progressive disease they will continue to be followed for disease assessments for 12 months after the End of Treatment visit, and for EFS until the end of study or study closure.

The expected duration of study will be 5 years, including enrollment (2 years), treatment (at least 1 year) and follow-up and EFS (2 years).

In the event of a study closure, participants currently receiving study drug will stop taking study drug and complete an abbreviated End of Treatment visit. Follow up and EFS will not continue after the End of Treatment visit.

5.6 Criteria for Removal from Study

Participants will be removed from study under the following circumstances:

- Disease progression or start of new therapy of CLL/NHL
- Participant decides to withdraw from the study
- Pregnancy
- Patient is off treatment and has been on study for at least 4 years since the date of consent
- Study closure

The reason for study removal and the date the participant was removed must be documented in the study-specific case report form. Alternative care options will be discussed with the participant.

In the event of unusual or life-threatening complications, a lead PI ([name].) needs to be immediately notified at [contact].

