7.2 Adverse Event Characteristics

An AE is any unfavorable and unintended sign, symptom, or disease temporally associated with the use of an investigational medicinal product or other protocol-imposed intervention, regardless of attribution. An abnormal laboratory value will not be assessed as an AE unless that value leads to discontinuation or delay in treatment, dose modification, therapeutic intervention, or is considered by the investigator to be a clinically significant change from baseline

This includes the following:

- AEs not previously observed in the patient that emerge during the protocol-specified AE reporting period, including signs or symptoms associated with NHL/CLL that were not present prior to the AE reporting period.
- Complications that occur as a result of protocol-mandated interventions (e.g., invasive procedures such as cardiac catheterizations).
- If applicable, AEs that occur prior to assignment of study treatment associated with medication washout, no treatment run-in, or other protocol-mandated intervention.
- Preexisting medical conditions (other than the condition being studied) judged by the investigator to have worsened in severity or frequency or changed in character during the protocol-specified AE reporting period.

Adverse events will be graded according to the NCI Common Toxicity Criteria Version 4.03. A copy of the CTC version 4.0 can be downloaded from <http://ctep.info.nih.gov>. Reporting of AEs will begin following the first dose of entospletinib and continue until End of Treatment visit. AEs after the End of Treatment visit should also be reported if considered related to study drug.

Safety is the primary study endpoint and will be assessed continuously. The safety profile will be assessed from the findings of physical examination, laboratory data, electrocardiograms (ECG), concomitant medications and treatments, and date of treatment withdrawal and cause. The safety profile will be based on incidence, severity, and cumulative nature of AEs. Adverse event seriousness, severity grade, and relationship to study medications will be assessed by the lead PI.

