All subjects who completed 1 cycle of therapy or who did not complete 1 cycle of therapy (or the run-in phase) because of a DLT will be considered evaluable for toxicity. All AEs, with the exception of progressive disease, will be reported from the start of therapy until the End of Treatment visit or until the start of an alternative systemic anti-leukemic therapy, if it occurs earlier.

All grade 3 or Grade 4 AEs considered related to study regimen must be followed until recovery to Grade ≤ 1 or baseline. The unresolved aforementioned events will be followed until, in the opinion of a lead PI (in discussion with a treating physician), resolution can no longer be expected.

All grade 3 and 4 hematological and non-hematological adverse events will be recorded on the case report forms.

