7.2.4.1. Adverse Event Reporting Period

The study period during which all AEs and SAEs must be reported begins after informed consent is obtained and initiation of study treatment and ends 30 days following the last administration of study treatment or study discontinuation/termination, whichever is earlier. After this period, investigators should only report SAEs that are attributed to prior study treatment. From the time of consent to the initiation of treatment, any AEs and SAEs related to study procedures should be reported.

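### Sections 5.5 and 5.6 disagree on whether a patient who progresses with open toxicity stays on study, and the end of AE reporting is defined in three ways

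*Combined protocol and SAP*

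**What the plan says.** **How long a patient is on study.** Section 5.5 gives the end as progression or "until study drug-related toxicities have resolved or are deemed irreversible by the sponsor-investigator (in discussion with a treating physician), whichever is later", with study closure as the other end point. Section 5.6 lists "Disease progression or start of new therapy of CLL/NHL" among the circumstances in which a participant is removed from study. It makes no exception for an open toxicity, and it requires the removal date on the case report form.

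**How long AEs are reported.** Three rules appear:

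- Section 7.2.4.1: the period for all AEs and SAEs "ends 30 days following the last administration of study treatment or study discontinuation/termination, whichever is earlier". After that, "investigators should only report SAEs that are attributed to prior study treatment".
- Section 7.2, on grading and reporting: "Reporting of AEs will begin following the first dose of entospletinib and continue until End of Treatment visit". It adds: "AEs after the End of Treatment visit should also be reported if considered related to study drug". Table 10 places that visit 8 weeks after the last dose, within 7 days either way.
- Section 7.2, on evaluability: all AEs except progressive disease are reported to the End of Treatment visit, or to the start of another systemic anti-leukemic therapy if that comes first. Progression is not a stopping point.

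**How long open events are followed.** Section 7.2 says "All grade 3 or Grade 4 AEs considered related to study regimen must be followed until recovery to Grade" 1 or below, or baseline, or until resolution is no longer expected. Section 10.2.1 follows related events ongoing at the End of Treatment visit until they resolve or are judged irreversible, except under early study closure.

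**The concern.** For a patient who progresses with a drug-related event still open, 5.5 and 5.6 give opposite instructions. The AE window in 7.2.4.1 refers to study discontinuation, so 5.6 may also decide when routine AE collection ends. Section 7.2 would continue that collection to a later date.

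Safety and tolerability by AEs is a Phase II secondary endpoint (1.2, 13.2.2), summarised for every treated patient (13.3, 13.4.2). If sites choose different rules, or apply 5.6 strictly, the length of AE collection depends on why the patient stopped. In a single-arm study of 17 patients, a few shortened windows can change the reported rates.

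Late-onset neutropenia shows how. Section 7.2.3 selects it for additional data collection or analysis and defines it as occurring 28 days or more after obinutuzumab ends. Suppose a patient stops both drugs at progression during cycles 1–6 and is removed that day. Under the strictest reading of 7.2.4.1, a non-serious case would fall outside the window. Under 7.2 it would be reported.

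**Working it through.** No sample size or error rate is involved. The check sets the rules side by side and counts days.

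**Step 1. Time on study (5.5 against 5.6).** Let P be the day of progression and R the day the last drug-related toxicity resolves or is judged irreversible.

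- Section 5.5: on study until max(P, R).
- Section 5.6: removed at P.

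If R ≤ P, both give P. If R > P, 5.5 gives R and 5.6 gives P, and the gap R − P has no stated limit. The conflict is therefore confined to patients who progress with an open drug-related toxicity.

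**Step 2. The AE window.** Let L be the last dose and D the day of study discontinuation. The sentence in 7.2.4.1 can be read in two ways:

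- Reading A: the window ends at min(L + 30, D).
- Reading B: the window ends at min(L, D) + 30.

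A patient takes no study dose after leaving the study, so L ≤ D. Reading B therefore always equals L + 30, and the words on discontinuation do nothing. Only reading A gives them effect.

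Assume progression, removal and last dose fall on the same day (D = L), and that study discontinuation includes removal of an individual under 5.6:

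| Rule | End of routine AE reporting, days after last dose |
|---|---|
| 7.2.4.1, reading A | min(30, 0) = 0 |
| 7.2.4.1, reading B | 30 |
| 7.2 with Table 10 (End of Treatment visit) | 8 × 7 = 56; with ± 7 days, 49 to 63 |
| 7.2, with the cut at new systemic therapy | 49 to 63, or the start of that therapy if earlier |

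Reading A falls short of reading B by 30 − 0 = 30 days. It falls short of the End of Treatment rule by 49 to 63 days, less if new systemic therapy starts first. If removal comes some days after the last dose, the shortfall is smaller by that number of days, and against reading B it is nil from day 30.

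**Step 3. What is still captured after removal, even under reading A.**

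- SAEs attributed to study treatment: yes (7.2.4.1, and the post-study paragraph of 7.2.5.2).
- Open related Grade 3–4 events: 7.2 requires follow-up with no stop at progression, but 5.6 has by then taken the patient off study.
- New related non-serious AEs: reportable under 7.2, not under 7.2.4.1.
- Unrelated AEs and unattributed SAEs: reportable under 7.2 to the End of Treatment visit or new systemic therapy, not under 7.2.4.1.

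**Step 4. How many patients.** The documents give no rate of progression with open toxicity. For illustration only, section 2.2.4 reports 24-week PFS of 70.1% (95% CI 51.3% to 82.7%) for entospletinib alone in CLL. With 17 patients:

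- (1 − 0.701) × 17 = 5.1 patients with a PFS event by week 24.
- At the interval limits, (1 − 0.827) × 17 = 2.9 and (1 − 0.513) × 17 = 8.3.

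On that assumption, about 5 is an upper bound by week 24 for progressors with open toxicity. It counts every PFS event whether or not a toxicity is open, and the combination may do better than entospletinib alone.

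**The case against.** The best defence is that the protocol protects these patients elsewhere, and that removal under 5.6 was meant to end disease follow-up only. Section 7.2 reports AEs to the End of Treatment visit without stopping at progression and requires related Grade 3–4 events to be followed. Section 10.2.1 follows related events open at that visit. Section 7.2.5.2 expects attributed SAEs to be reported even after participation ends. The sentence in 7.2.4.1 can be read to leave 30 days. Section 5.6 speaks of removal and 5.7 uses trial discontinuation as its own heading, so discontinuation in 7.2.4.1 need not mean removal of one patient.

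Much of this stands. It rules out several stronger conclusions that a reader might infer:

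- *Safety follow-up is cut for all who progress.* This needs reading A and an unstated meaning of discontinuation, and it sets aside 7.2, 7.2.5.2 and 10.2.1.
- *The End of Treatment visit is lost.* Section 10.2.1 and the footnote to Table 10 except only study closure. Section 5.5 limits the later 12 months of disease assessment to patients who stop for reasons other than progression, but says nothing against the visit itself. What is unclear is whether a patient already removed attends it. Section 13.3 mentions an early termination visit that the schedule does not contain.
- *The RP2D is affected.* It rests on DLTs in the run-in and cycle 1 (5.1.1, 5.2).
- *Every progressor loses follow-up of a Grade 3–4 event.* Only those with such an event open could.
- *A planned comparison is biased.* Section 13.4.2 summarises safety by phase and dose level, not by reason for stopping.

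The defence does not remove the contradiction. The protective passages are the other half of it, since they ask for follow-up of patients whom 5.6 has taken off study.

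**Conclusion.** The point holds as an inconsistency that should be corrected. Sections 5.5 and 5.6 cannot both be followed for a patient who progresses with an open drug-related toxicity, and the end of AE reporting has three definitions.

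The largest consequence is that routine collection of non-serious AEs and unattributed SAEs ends on the day of removal, 30 days short of one rule and up to 49 to 63 days short of another. It rests on three assumptions: reading A of 7.2.4.1, discontinuation including removal under 5.6, and removal coinciding with the last dose. Reading A is the more natural because the alternative leaves the clause without effect. The second assumption is not stated anywhere.

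The number of patients affected is unknown. The effect on reported AE rates can be described in direction (under-ascertainment after removal) but not in size.

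**What to change.** Reconcile 5.5, 5.6, 7.2, 7.2.4.1 and 10.2.1 in one amendment:

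1. In 5.6, state that progression or new therapy ends efficacy follow-up but not the safety follow-up that 5.5, 7.2 and 10.2.1 already require.
2. State one end of AE reporting and use it in both places in 7.2 and in 7.2.4.1. It should not depend on the reason for stopping, except for withdrawal of consent and study closure. Deleting the discontinuation clause from 7.2.4.1 is not enough, because the 30-day, End of Treatment and new-therapy rules would still conflict. The cut at new systemic therapy therefore needs an explicit decision.
3. Say whether a patient removed at progression attends the End of Treatment visit, and align 13.3 with the schedule.

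The cost is a few wording changes and a few safety contacts after progression, which 5.5 and 7.2 already call for. No dose, treatment rule or sample size changes.

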5.7 Trial Discontinuation

The trial will cease when participants

- have started a subsequent treatment for CLL, or
- have been followed for 3 years since beginning of therapy, and are no longer receiving therapy,
or
- have died of any cause
- come off study due to study closure

The last scheduled follow-up will occur on a post-treatment visit as defined in study procedures.

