10.1 Screening/Baseline Visit

During the Pretreatment Period, subjects are screened and consented for the study. Informed consent must be obtained before initiation of any clinical screening procedure that is performed solely for the purpose of determining eligibility for this research study. Evaluations performed as part of routine care before informed consent can be utilized as screening evaluations if done within the defined time period. Informed consent should be obtained within 30 days before the first dose of study treatment.

Subjects will undergo screening evaluations to determine study eligibility. All qualifying screening and eligibility assessments must be performed within 30 days before the first dose of study treatment. Tests used for baseline disease assessments must be performed within specified time frame of the initial dose of study treatment. Refer to section 10.4 and 10.5. Those assessments will be performed at OHSU or the participating sites. However, results provided by other institutions are acceptable as long as they satisfy the timing criteria.

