10.2 Treatment Period

Clinic visits will be performed every cycle on Day 1. Under certain circumstances (e.g., clinic holiday, inclement weather) Day 1 may be delayed by not more than 3 days or occur earlier than scheduled by not more than 3 days during cycles 2-12; Days 8 and 15 of Cycle 1 may be delayed by 1 day or occur 1 day early.

Clinical laboratory assessments are to be collected on D1 of each cycle visit, or \leq 48 hours before those visits, and the test results must be available and reviewed before obinutuzumab is given (C1-6). Screening assessment tests can be considered as Day -7 tests (start of treatment) if performed \leq 72 hours before the first dose of study treatment; otherwise, the required evaluations must be repeated within this timeframe.

On Day -7 and C1D1 all patients with CLL/SLL will provide samples for biomarker analysis.

After the initial 12 treatment cycles subjects in whom it is clinically safe to do so, are benefitting from entospletinib, and who desire to continue entospletinib monotherapy may continue entospletinib therapy beyond the initial twelve cycles, with approval from the treating physician and sponsor-investigator, until disease progression or removal from treatment (see Section 5.4).

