13.2.2 Secondary Endpoints

Secondary endpoints of phase 2 portion of study are the following:

- Objective response rate (ORR)
- Event free survival defined as the interval between the date of first study treatment and the date of objective signs of disease recurrence, subsequent anti-leukemic therapy, or death, whichever is first reported EFS will be censored if entospletinib is discontinued for other reasons (such as drug is no longer available)
- Safety and tolerability of entospletinib in combination with obinutuzumab by AEs

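### Sections 5.5, 5.6 and 5.7 set three incompatible EFS follow-up limits for patients off drug, and two of them apply only off therapy, so Kaplan-Meier EFS beyond about 3 to 4 years can be biased

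*Combined protocol and SAP*

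**What the plan says.** Four places bear on how long an event-free patient who is off drug is followed for EFS.

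- Section 5.5 follows patients who stop for reasons other than progression "for 12 months after the End of Treatment visit, and for EFS until the end of study or study closure". The EFS entry in section 10.4 and Table 10 agree: assessments continue every 6 months after the first year, with no end other than study closure.
- Section 5.6 removes a patient from study when "Patient is off treatment and has been on study for at least 4 years since the date of consent".
- Section 5.7 says the trial ceases when participants "have been followed for 3 years since beginning of therapy, and are no longer receiving therapy".
- Section 13.2.2 measures EFS from first study treatment and adds that EFS is censored when entospletinib is discontinued for other reasons, with loss of drug supply as the example.

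Neither 5.6 nor 5.7 sets a time limit for a patient still on drug. Under section 10.2, patients who are benefitting, for whom it is safe and who wish to go on "may continue entospletinib therapy beyond the initial twelve cycles", with approval from the treating physician and the sponsor-investigator.

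Section 13.4.2 summarises EFS descriptively by Kaplan-Meier. No landmark time and no test are stated.

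**The concern.** The three limits cannot all be followed for the same patient, and 5.6 counts from consent although EFS counts from first treatment.

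The 3-year and 4-year limits also depend on treatment status. Read literally, an event-free patient off drug leaves the risk set at the limit, while one on drug stays. A patient who stops after the limit is censored on stopping. Kaplan-Meier assumes that those censored have the same later event risk as those who remain. Here, those who remain were allowed to continue partly because they were doing well.

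At stake is the tail of a secondary endpoint. Section 13.4.3 also uses that endpoint in the biomarker and prior-kinase-inhibitor subgroups, where numbers are smaller still.

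**Working it through.** **1. The stated duration.** Section 5.5 gives 2 years' enrollment + at least 1 year's treatment + 2 years' follow-up and EFS = 5 years, which reproduces the stated total. Potential follow-up from first dose therefore runs from 5 - 2 = 3 years (last enrolled) to 5 years (first enrolled). Both limits fall inside the planned study.

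**2. The limits on the EFS time scale.** Section 10.1 says: "Informed consent should be obtained within 30 days before the first dose of study treatment". Four years from consent is thus 4 - 30/365.25 = 3.92 to 4.00 years from first dose. The gap to the 5.7 limit is (3.92 - 3) x 12 = 11.0 to 12.0 months.

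**3. Size of the possible error.** The documents give no event rates by drug status, so these inputs are assumptions:
- uniform accrual over 2 years and closure at 5 years;
- half of patients stop at the end of cycle 12 (343/365.25 = 0.94 years, counting the run-in), and the rest stop at 0.3 per year;
- on-drug event hazard 0.7 x 0.312 = 0.218 per year. The 0.312 is ln 2/(26.7/12), from the 26.7-month median PFS quoted in section 2.3.2.2 for another regimen in untreated patients;
- off/on hazard ratio of 0.5, 1, 2 or 3.

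Kaplan-Meier EFS at 4 years in a large-sample simulation:

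| Off/on hazard ratio | True | 5.5 (to end of study) | 5.7 (3 years) | Error under 5.7 | 5.6 (about 4 years) | Error under 5.6 |
|---|---|---|---|---|---|---|
| 0.5 | 0.529 | 0.529 | 0.484 | -4.5 points | 0.524 | -0.5 |
| 1 | 0.418 | 0.418 | 0.418 | 0 | 0.418 | 0 |
| 2 | 0.278 | 0.278 | 0.322 | +4.4 | 0.281 | +0.3 |
| 3 | 0.201 | 0.202 | 0.259 | +5.8 | 0.206 | +0.5 |

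The 5.7 column can be checked by hand. After 3 years only on-drug patients remain, so KM(4) = S(3) x exp(-0.218) = S(3) x 0.804. With simulated S(3) of 0.602, 0.519, 0.401 and 0.321, this gives 0.484, 0.417, 0.322 and 0.258, which agrees to rounding.

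EFS at 2 and 3 years is identical under all three rules. At 4.75 years the 5.6 limit gives errors of -3.7, 0, +2.9 and +3.4 points, but only patients enrolled in the first 0.25 of 2 years can be followed that long (17 x 0.125 = 2.1 of 17, before any events).

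**4. Loss of information, even without bias.** At 3.25 years with equal hazards, the expected number at risk is 17 x exp(-0.218 x 3.25) x (1.75/2) = 17 x 0.492 x 0.875 = 7.3 without a limit. Under 5.7 only those still on drug count, a share of 0.5 x exp(-0.3 x 2.31) = 0.25, which leaves 1.8.

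**5. The 13.2.2 censoring rule.** Read broadly, so that any event-free stop censors, it acts earlier and more strongly: at ratio 2, 3-year EFS is 0.52 against a true 0.40.

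**The case against.** The strongest reply is that 5.7 is headed as trial discontinuation. It could be a trial-level end condition, with 5.6 as the patient-level removal rule; 3 years is also the follow-up that the last-enrolled patient would reach. That reading does not remove the problem. The items in 5.7 describe individual participants and still turn on whether they are receiving therapy, and 5.6 still conflicts with 5.5.

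A reader might infer that late EFS is biased upward. The documents do not support that as a fact. It needs a higher event rate off drug than on drug, and neither rate is given. Patients off drug include those who completed the planned 12 cycles, and continuation also depends on safety, preference and approvals. The error is zero at equal hazards and negative if patients who stop do better.

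A reader might also infer that EFS follow-up simply ends at 3 years, or that sites already apply different limits. Section 5.5 and the schedule contradict the first, and nothing in the documents shows the second.

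The practical reach is limited, and this part of the objection stands. EFS is descriptive with no late landmark, and few patients would be at risk in the tail. A median beyond 3 years also looks unlikely on the documents' own benchmarks. Assuming a constant hazard, the 70.1% PFS at 24 weeks in section 2.2.4 implies a median near 47 weeks and about 10% at 3 years; the 26.7-month median implies about 39%. The error scales with 3-year EFS. At 10%, with year-4 conditional risks unchanged, the +4.4 and +5.8 points become 0.10 x 4.4/0.401 = 1.1 and 0.10 x 5.8/0.321 = 1.8.

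Finally, if 13.2.2 is read broadly, event-free patients are already censored on stopping and the limits add nothing further. That is a reason to include 13.2.2 in the correction, not to leave the limits as they are.

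**Conclusion.** The point holds as a conflict in the text with a bounded statistical consequence. Three sections give three EFS limits for the same patient; two of them differ by 11 to 12 months and apply only off therapy. Applied as written, they make Kaplan-Meier EFS beyond 3 years (5.7) or about 4 years (5.6) an estimate from on-drug patients alone.

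Upward bias is plausible but not established. The 4-year range of -4.5 to +5.8 points under 5.7 rests on the assumed stopping pattern, hazards and accrual above, and would change with them. The absence of any effect before the limit does not depend on those assumptions. The primary CR analysis is untouched. The correction should be made, but it does not threaten the trial's main conclusion.

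**What to change.** - In 5.5, 5.6 and 5.7, state one EFS horizon measured from first study treatment, applying equally to patients on and off drug.
- In 13.2.2, reconcile the censoring rule with that horizon, so that stopping entospletinib for other reasons does not by itself censor EFS while the patient is still followed. Censoring when study closure ends all follow-up can remain.
- In 13.4.2, administratively censor every event-free patient at the horizon and report no EFS rate or median beyond it.

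The cost is protocol and SAP wording. With the shorter stated limit (3 years) no visits are added, and on the planned timeline even the last-enrolled patient could reach it. With the longer limit, the existing 6-monthly EFS contacts continue for about another year, one or two per patient. The price is that EFS beyond the horizon is not reported. Follow-up of on-drug patients for other purposes, such as safety, can continue.
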